4.5 Expected duration of participation of female patients in the study

Screening period (up to 15 days before the surgery)

Treatment period (Day 0)

Interim safety evaluation (Day 6±1)

Evaluation of treatment efficacy (Day 30±4 days)

Considering the given periods, the minimum duration of the study for female patient is 28 days, and the maximum duration is 50 days.

4.6 Description of “termination rules” or “withdrawal criteria” for separate subjects or the study, in general.

Withdrawal criteria for separate subjects of the study are described in section 5.3.

According to the Article 40 of the FL No 61-Φ3 “On drug circulation” dated 12.04.2010 as amended and the requirements of the Good Clinical Practice of the Russian Federation, approved by the order of the Ministry of Health of the RF dated 19.06.2003 No 266, a clinical study may be discontinued or terminated, if in the process of its performance, hazard to life, health of patients is revealed. In case of revealed hazard to life, health of a female patient of the clinical study, investigators are obliged to inform on this a head of healthcare institution or organization that obtained permission of authorized federal agency for conducting the clinical study of the drug. Decision on discontinuation of the clinical study of the medical drug is made by a head of the healthcare institution and (or) the Sponsor of the study (or CRO)¹, decision on termination of such a study is made by an authorized federal agency based on written report by the head of medical organization or organization of the study Sponsor (or CRO).

Report on completion, discontinuation or termination of the clinical study of the medical drug is sent to an authorized federal agency as per the form established by it within five working days from the date of such completion, discontinuation or termination of the clinical study.

The Investigator must immediately inform the study subjects on discontinuation or termination of the study, provide them adequate medical care and follow-up. Upon termination of the study the Investigator must assure that interests of the study subjects are adequately protected.

¹ Organization obtained permission from an authorized federal agency for organization of the clinical study of the medical drug.

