All ARs developed during the study in female patients withdrawn from the study, including ARs to the moment of terminating participation of female patient in the study will be analyzed and included into a final report on the study performance.

If withdrawal/exclusion from the study was after administration of the study drug to a female patient, her data collected before the moment of withdrawal/exclusion from the study will be analyzed during analysis of safety and, if possible, during analysis of efficacy. Approaches to analysis of data on the study participants early terminated their participation in the study are described in section 9.5.

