5.3.4 Follow-up of female patients early terminated the study

Follow-up of female patients withdrawn from the study is not planned intentionally. See also section 4.2.4.4.

If a female patient was withdrawn from the study due to the reason of AR/SAR, she is followed up due to resolution of the AR/SAR or until the Investigator considers it to be “chronic” or “stable”. The follow up of female patients of the study withdrawn from the study and, in the meantime, having ARs or having other parameters of safety, which could cause therapy termination, is described in section 8.4.

6 Treatment of the study subjects

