8.2 Methods and terms of evaluation, recording and analysis of safety parameters

Evaluation of safety of the study drugs Seroguard, solution 0.41 g/L (JSC Pharmasyntez, Russia) and the Placebo will be performed for all the study subjects at Visits 1-3, based on account of parameter, specified in section 8.1. Detection of adverse reactions (ARs) happens from the moment of signing informed consent to visit 3 inclusive. In addition, each study subject will be provided a phone number of the Investigator for contact in case of any problems with health. Clinical symptoms that will be developed after signing informed consent, but before use of the test drug or the placebo will be recorded as concomitant disease.

If the Investigator finds/receives information on AR, an unscheduled visit at the study site will be appointed in the nearest time (if required). At the moment of receiving information on AR, after analysis of AR and evaluation of risk for the study subject, the Investigator comes to a decision on delivery of required medical care. At the unscheduled visit, the Investigator makes decision on possibility of further participation of female patient in the study.

In case of indications, by the decision of the Medical Investigator or the physician, additional clinical and/or laboratory-instrumental investigations may be performed at unscheduled visits (see section 4.2.4.5).

The Investigator is responsible for notification of the Sponsor on any event considered as unusual, even if this event may be considered as unexpected benefit for the study subject.

Adverse reactions

AR means “any unintended and unfavorable reaction of the body which may be related to the drug administration” (Federal Law dated 12.04.2010 No 61-Φ3 “On drug circulation”).

AR severity grades

AR severity grade will be established as per the below classification:

- **Grade 1: mild.** Asymptomatic (detected at physical or laboratory-instrumental investigation) or with minimally pronounced symptoms, easily tolerable by a subject, causing minimum discomfort and not interfering with normal activity, not requiring special treatment;

- **Grade 2: moderate.** Causing discomfort, limiting normal activity; requiring medical aid without invasive interventions (for example, applying a dressing);
- **Grade 3: severe.** Making normal activity impossible; disabling; requiring invasive intervention; requiring hospitalization; life-threatening; death.

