Causal relation of AR to administration of the study drugs

Causal relation of AR to administration of the study drugs will be evaluated based on criteria of the World Health Organization (WHO):

- **Definite.** Clinical manifestations of AR, including laboratory abnormalities, observed during administration of the drugs, which may not be explained by presence of current diseases and influence of other factors and chemical compounds. Side reaction manifestation regress after the drug withdrawal and develop after re-administration.
- **Probable.** Clinical manifestations of AR, including laboratory abnormalities, related to time of the drug administration, which are unlikely related to concomitant diseases or other factors and which regress after the drug withdrawal. Response reaction to re-administration is unknown.
- **Possible.** Clinical manifestations of AR, including laboratory abnormalities, related to time of the drug administration, which may be explained by presence of concomitant diseases or administration of the other drugs and chemical compounds. Information on reaction to withdrawal of the drug is unclear.
- **Unlikely.** Clinical manifestations of AR, including laboratory abnormalities, which develop with no clear temporary relation to the drug administration; there are other factors (drugs, diseases, chemical substances), that may be a reason of their development.
- **Conditional.** Clinical manifestations of AR, including laboratory abnormalities, related to “side reactions”, that require obtaining additional data (for accurate estimate) or these obtained data are analyzed at present.
- **Unclassified.** Reports on suspected side reaction may not be evaluated, because the information is not sufficient or it is contradictory.

Serious adverse reaction or unexpected adverse reaction

Serious AR (SAR) is an adverse reaction of the body related to the administration of the drug that led to death, congenital anomaly or birth defects or life-threatening, requiring hospitalization or incapacitating and (or) disabling (Federal Law dated 12.04.2010 No 61-Φ3 “On drug circulation”).

In case of SAR development in the study subject, administration of the study drug is discontinued, the Medical Investigator completes the respective section of the CRF of the study subject and SAR Report Form.

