If any AR develops, the Investigator should complete the respective sections of the CRF of the study subject, evaluate feasibility of continuing the study by female patient (exclude the study subject or continue participation of female patient in the study). ARs will be recorded from the moment of the study drug administration and to completion of the final visit (Visit 3).

For each AR, the following information should be recorded in the primary medical documentation:

- AR nature as per the ICD-10 terminology system (International Classification of Diseases 10th revision);
- severity grade (mild/ moderate/ severe AR);
- causal relation to administration of the test drug/reference drug (definite/ probable/ possible/ unlikely/ conditional/ unclassified);
- duration (start date and time / stop date and time);
- outcome (resolved/ resolving/ resolved with sequelae/ not resolved / lethal outcome/ no data);
- is AR serious.

Report on serious adverse reaction to the Sponsor

In case of SAR, it is necessary to record the fact of SAR development in the primary documentation and complete respective pages of the CRF of the study subject.

Information on SAR should be sent to the pharmacovigilance officer of JSC Pharmasyntez, [name] within 24 hours:

- [contact];
- [contact];
- E-mail: [contact].

A special form of serious adverse reaction is completed in this case (see section 17.1), original of which is sent to JSC Pharmasyntez to the following address: [name].

Notification form should be sent, even if the Investigator has incomplete volume of information on SAR. However, after the primary report on SAR, the Investigator should always inform on evaluation of degree of SAR relation to the administration of the study drug (see section 8.2). The Investigator should receive confirmation that the information is delivered.

If provided by the current requirements, the Sponsor will send respective notifications on AR to appropriate healthcare authorities.

Pregnancy during the study

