Before the study beginning, female patients are instructed on effective methods of contraception used throughout the study. All the study subjects pass pregnancy test at Visit 0, 3 or at Withdrawal Visit (see section 4.2.3.5), they are also instructed on required obligatory notification of the Investigator at any time when pregnancy is suspected. In this case, during the next/unscheduled visit, a pregnancy test is repeated (using test-strip, see section 4.2.3.5) and, if required, a concentration of beta-chorionic gonadotropin in blood is determined, and examination by gynecologist is performed. If fact of pregnancy is confirmed, female patient discontinues her participation in the study (see section **Ошибка! Источник ссылки не найден.**).

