8.4 Method and duration of follow-up of the study subjects after adverse reactions

Information on all newly developed/continuing ARs is recorded at each next/unscheduled visit. In case of repeated report on continuing AR, it is necessary to complete a new template of AR Report Form with note of date of a primary report on continuing AR.

All ARs should be traced until their resolution or until the Investigator considers them as “chronic” or “stable” (AR outcomes in such cases are classified as resolving/resolved with sequelae/ not recovered). Information on this should be recorded in the primary documentation, CRF of a female patient and the final AR Report Form.

At the final visit (Visit 3), the Investigator instructs the study subject on necessity to report on any ARs subsequently which, in the opinion of a female patient or her physician may be related to the administration of the test drug/reference drug.

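### Dosed women who are withdrawn are not actively asked about new adverse reactions up to Day 30±4, the protocol's follow-up statements conflict, and pregnancy outcome is not followed

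*Protocol*

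**What the plan says.** **General window.** Section 8.2: "Detection of adverse reactions (ARs) happens from the moment of signing informed consent to visit 3 inclusive". Section 8.3 also ends recording at Visit 3, but starts it at drug administration. Visit 3 is at Day 30±4. Neither section makes an exception for withdrawn women.

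**Withdrawn women.** Four places bear on them:
- Section 5.3.2, first statement: ARs in withdrawn women, "including ARs to the moment of terminating participation of female patient in the study will be analyzed", go into the final report.
- Section 5.3.2, next paragraph: for a woman withdrawn after dosing, the safety analysis uses what was collected before she left.
- Section 5.3.4: "Follow-up of female patients withdrawn from the study is not planned intentionally". It makes an exception for women withdrawn because of an AR, and it refers the reader to 4.2.4.4.
- Section 4.2.4.4: a withdrawal visit with AR evaluation takes place the same day if she is in hospital, or within 5 days of the withdrawal becoming known if she has been discharged. A reluctant patient may give AR information only, or in exceptional cases be reached by phone. The section then promises follow-up for patients withdrawn voluntarily and with ARs, until recovery, stabilisation or chronicity.

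**Later reporting.** Section 8.4: "At the final visit (Visit 3), the Investigator instructs the study subject on necessity to report on any ARs subsequently".

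**Pregnancy.** Section 8.3: "If fact of pregnancy is confirmed, female patient discontinues her participation in the study". The pregnancy text ends there. The seriousness definition in 8.2 covers reactions that "led to death, congenital anomaly or birth defects or life-threatening, requiring hospitalization", and the report form in 17.1 has a box for congenital anomaly.

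**Analysis.** Section 9.1.4 reports AR and SAR (serious AR) frequencies with 95% confidence intervals and compares them by Fisher's exact test. Under 9.7.1 and 9.7.3 the safety set is every randomised woman who received study drug.

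**The concern.** Exposure is one intraoperative instillation, so a woman who leaves on Day 6 has had the same dose as one who completes. If nobody asks her about new events after that, she still counts in the denominator, and the unobserved days are treated as event-free. The percentages in objectives 10 to 16 would then rest on windows running from the day of surgery up to 26 to 34 days.

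The shortened windows may also fall on informative patients. Reasons for leaving include repeat surgery before Visit 3, pregnancy and situations that threaten safety (5.3, 5.3.1), and new use of a forbidden drug (6.2.2). No later analysis can recover events that were never asked about, so this cannot be left to a statistical analysis plan.

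For pregnancy, the protocol names a serious outcome but plans no active way to learn of it. The draft insert in 2.1 says the drug has not been tested in pregnant patients.

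**Working it through.** **Step 1. The text side by side.** Take a dosed woman withdrawn by the investigator with no AR present.
- Under 8.2 and 8.3 the window runs to Visit 3.
- Under 5.3.2, second paragraph, only data up to withdrawal are used. It is unclear whether an AR first reported at the withdrawal visit counts.
- Under 5.3.4 she is not followed.
- Under 4.2.4.4 the answer depends on whether voluntary withdrawal and having an AR are joint or alternative conditions. On either reading she is not covered. The stated end-point (recovery, stabilisation, chronicity) describes tracing an existing AR, not looking for new ones.

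So no section gives her a scheduled question about new ARs after the withdrawal visit, and the sections do not agree with one another.

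**Step 2. How many women.** Inputs from 9.2: 26 randomised and 24 completed per arm, four arms, 10% loss after randomisation.
- Check of the plan's figure: 24 / (1 − 0.10) = 26.7, which rounds up to 27; the plan states 26. The loss implied by 26 and 24 is 2/26 = 7.7%.
- On the stated counts: 2 per arm, 4 × 2 = 8 of 104.
- At the full 10%: 0.10 × 26 = 2.6 per arm, 0.10 × 104 = 10.4 in all.

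**Step 3. Largest possible understatement.** A woman with a shortened window can change an arm's percentage only if her recorded status should have been yes and is no. With k such women among 26 dosed, the bound is k/26.
- k = 1: 1/26 = 3.8 points
- k = 2: 2/26 = 7.7 points
- k = 2.6: 2.6/26 = 10.0 points
- k = 3: 3/26 = 11.5 points

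These bounds take every withdrawn woman to have been dosed. If one of the two left before dosing, the bound is 1/25 = 4.0 points; if both did, it is zero.

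**Step 4. Observation time lost.** Full observation per arm is 26 × 30 = 780 person-days. With 2 withdrawals on day d, the observed time is 24 × 30 + 2 × d. The withdrawal day is an assumption, so a range is shown.

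| Withdrawal day | Person-days observed | Lost |
|---|---|---|
| 0 | 720 | 7.7% |
| 6 | 732 | 6.2% |
| 15 | 750 | 3.8% |

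**Step 5. Pregnancy.** The documents give no pregnancy rate, so no expected number of pregnancies or anomalies can be computed. The point rests on the text alone: testing, confirmation and discontinuation are described, and outcome is not.

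**The case against.** Much can be said for the protocol.

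- **Section 5.3.2.** A reader might take its sentence on ARs in withdrawn women as stopping collection at the moment of leaving. It does not: the wording is inclusive. The restriction comes from the following paragraph and from 5.3.4.
- **Withdrawal visit.** It includes AR evaluation, laboratory tests, ECG and imaging, can fall some days after withdrawal, and existing ARs are traced beyond it. This stands, and the gap is limited to new ARs after that visit.
- **Reporting routes.** Every woman has the investigator's phone number (8.2), and completers are told at Visit 3 to report later ARs. A reader might infer that a birth defect could never be recorded. The documents do not support that: the 17.1 form provides for it, and a pregnancy first found by the Visit 3 test is found at the visit where that instruction is given. What is missing is active ascertainment. Mandatory contraception should also keep pregnancies few.
- **Size.** A reader might infer a large bias from Phase I, with 206 ARs in 47 patients. That is a count of events, not a per-patient risk, and the protocol gives no per-patient AR risk to apply here. Conversion or need for a drain can remove women before dosing, and events clustering soon after surgery would make the loss smaller.
- **Between-arm bias.** This would need unequal withdrawal or unequal late risk, and nothing in the protocol shows either.

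The objection that unequal observation time is a matter for the analysis plan stands only in part. The choice of summary can be left to that plan; whether anyone asks the woman cannot.

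**Conclusion.** The point holds in a limited form. After the withdrawal visit the protocol plans no active collection of new ARs in dosed women, its follow-up statements (4.2.4.4, 5.3.2, 5.3.4, 8.2, 8.3) cannot all be followed together, and pregnancy outcome is left to passive reporting.

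The effect on any AR or SAR percentage is bounded. At the protocol's own counts it is at most 7.7 points per arm, and at the full 10% loss about 10. These figures assume that every withdrawn woman was dosed and had an unrecorded event of the kind counted, and no recorded one, so the actual figure should be smaller. The efficacy conclusion is not affected. This is a cheap improvement, not a flaw that threatens the trial.

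**What to change.** Reconcile 4.2.4.4, 5.3.2, 5.3.4, 8.2 and 8.3 so that they state one rule:

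1. Every dosed woman who has not refused contact is asked about new ARs and SARs up to Day 30±4. A phone call is enough; 4.2.4.4 already accepts one in exceptional cases.
2. Events found this way count in the 9.1.4 frequencies, as do those first reported at the withdrawal visit.
3. In 8.3, a confirmed pregnancy is followed to its outcome, and any congenital anomaly is reported on the 17.1 form.

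The start of the AR window (consent in 8.2, drug administration in 8.3) can be aligned in the same edit.

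The cost is an amendment to the wording, about 8 to 10 phone calls across the trial, and outcome follow-up of any pregnancy. No extra patients, visits or procedures are needed for the AR part.

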5.3.3 Substitution procedure

Female patients withdrawn before randomization will be substituted by new female patients (in the volume considered by the calculated number of female patients screened). Female patients withdrawn from the study after randomization and beginning of the therapy will not be replaced by new ones, and their data will be considered in the final analysis (see section 9.5).

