4.2.4.2 Therapy period

Visit 1 (Day 0)

Before the surgery:

- Physical examination (see section 4.2.3.2).
- Evaluation of vital signs (see section 4.2.3.3).
- Actualization of the information on concomitant therapy.
- Actualization of the information on concomitant diseases.

- Re-evaluation of inclusion/non-inclusion criteria (see section 5).
- Randomization (see section 4.3.1).
- ***Surgical intervention using the test drug or the placebo***

After the surgery:

- Physical examination (see section 4.2.3.2).
- Evaluation of vital signs (see section 4.2.3.3).
- Evaluation of local status (condition of postsurgical wounds). (see section 4.2.3.4)
- Evaluation of AR (see section 8).

Visit 2 Interim safety assessment (Day 6±1)

- Physical examination (see section 4.2.3.2).
- Evaluation of vital signs (see section 4.2.3.3).
- Evaluation of local status (condition of postsurgical wounds). (see section 4.2.3.4) .
- Evaluation of withdrawal criteria (see section 5.3)
- Laboratory investigations: complete blood count, blood chemistry, urinalysis (see section 4.2.3.5).
- USI of the abdominal cavity (see section 4.2.3.6).
- ECG (see section 4.2.3.6).
- Actualization of the information on concomitant therapy.
- Actualization of the information on concomitant diseases.
- Evaluation of AR (see section 8).

Visit 3 (30±4) Evaluation of safety and efficacy

- Physical examination (see section 4.2.3.2).
- Evaluation of vital signs (see section 4.2.3.3).
- Evaluation of local status (condition of postsurgical wounds).
- Laboratory investigations: complete blood count, blood chemistry, coagulogram, urinalysis, pregnancy test (see section 4.2.3.5).
- USI of pelvic organs (transvaginal) (see section 4.2.3.6).
- MRI of the abdominal cavity and the pelvis (see section 4.2.3.6).
- ECG (see section 4.2.3.6)
- Actualization of the information on concomitant therapy.

- Actualization of the information on concomitant diseases.
- Evaluation of AR (see section 8).

4.2.4.3 *Unscheduled visit*

Unscheduled visit may be performed at the discretion of the Investigator in case of ARs for performance of the required investigations. During each unscheduled visit regardless of its reason, the Investigator performs the following procedures and completes respective pages of CRF (Additional/Unscheduled visit):

- Physical examination (see section 4.2.3.2).
- Evaluation of vital signs (see section 4.2.3.3).
- Evaluation of local status (condition of postsurgical wounds).

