- Evaluation of withdrawal criteria (see section 5.3)
- Laboratory investigations: complete blood count, blood chemistry, urinalysis (see section 4.2.3.5).
- ECG (see section 4.2.3.6).
- Actualization of the information on concomitant therapy.
- Evaluation of AR (see section 8).

If any indications, any study procedure may be performed additionally (see section 4.2.3). Respective pages of CRF are completed in this case.

4.2.4.4 *Withdrawal visit*

Medical aid is performed as per the standards accepted in the specific healthcare institution in case of withdrawal of patient from the study. Visit of withdrawal from the study will be similar to completion Visit 3 by contents.

- Physical examination (see section 4.2.3.2).
- Evaluation of vital signs (see section 4.2.3.3).
- Evaluation of local status (condition of postsurgical wounds) (see section 4.2.3.4) .
- Evaluation of AR (see section 8).
- USI of pelvic organs (transvaginal) (see section 4.2.3.6).
- MRI of the abdominal cavity and the pelvis (see section 4.2.3.6).
- USI of the abdominal cavity (see section 4.2.3.6).
- Laboratory investigations: complete blood count, blood chemistry, coagulogram, urinalysis, pregnancy test (see section 4.2.3.5).
- ECG (see section 4.2.3.6).

If a female patient is withdrawn from the study before discharge from the hospital, withdrawal visit is performed on the same day. If a female patient is withdrawn from the study already after discharge from the hospital, the visit should be performed within 5 days after it became known on withdrawal of a female patient. If a hospitalized patient refuses to pass the visit procedures, it may be limited by collection of information on AR. If an ambulatory patient refuses to come to a withdrawal visit, a phone contact (in exceptional cases) is accepted.

A follow-up will be performed for patients withdrawn from the study voluntarily and with ARs. The follow-up will last until recovery of the study patient condition, until stabilization or establishing chronic AR.

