8.5 Modification of the study drug dosage regimen

In the present study, modification of the study drug dosage regimen is not considered which is provided by the purposes and design of the present study.

9 Statistics

9.1 Description of statistical methods to be used, including terms of each planned interim analysis

Statistical analysis will be performed using a specialized software, selection of which will be performed at the stage of preparation of statistical analysis plan.

Continuous (quantitative) data will be presented using a number of observations, arithmetic mean, 95 % confidence interval (CI) for the mean (unless otherwise specified), standard (mean square) deviation, median, interquartile range, minimum and maximum.

Serial, categorical and qualitative data will be provided using absolute frequency (number of observations), relative frequencies (percent) and 95 % CI (unless otherwise specified).

Unless otherwise specified, in the plan of statistical analysis, statistical test will be bilateral with 5% confidence level.

Anamnesis and ARs will be coded using MedDRA classifier.

This section briefly describes the planned analysis. A complete analysis will be described in the plan of statistical analysis.

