- Expected rates of achieving the primary endpoint in the groups with different dosages will be considered initially equal
- First type error (α) = 5 % (0.05) for *superiority* hypothesis
- Second type error (β) = 20 % (0.2), that corresponds to 80 % power.
- Expected withdrawal from the study will make 15% at screening and 10% after randomization

Null and alternative hypotheses for the *superiority testing* stage are worded as follows:

1. Null hypothesis (H_0) holds that the difference in the rate of the primary endpoint achievement for one of the dosages of the drug Seroguard and the placebo will not exceed 5% in favor of the drug

$$H_0: p_1 - p_0 \leq 0.05$$

2. Alternative hypothesis (H_A) holds that the difference in the rate of the primary endpoint achievement of one of the dosages of the drug Seroguard and the placebo will exceed 5% in favor of the drug

$$H_A: p_1 - p_0 > 0.05$$

Where p_0 and p_1 are the rates of the primary endpoint achievement in the groups of the placebo and Seroguard (of any dosage), respectively.

For the purpose of calculation of the sample size in each group in this case, the formula is applied which is given in (33)

$$n = (p_1 \times (1 - p_0) + p_0 \times (1 - p_0)) \times \left(\frac{z_{1-\alpha} + z_{1-\beta}}{p_1 - p_0 - \delta} \right)^2$$

where

n is the size of one group;

z is the value of the normal distribution function with the given α and β levels;

δ is superiority margin - 5%;

p_1 is the expected percentage in the active drug group (one of the dosages) – 45%

p_0 is the expected percentage in the placebo group – 5%

Applying the above data into this formula, we obtain the minimum number of patients in the placebo group without considering withdrawal: 24 completed cases which corresponds to 26 randomizations and 30 screenings.

Thus, the total number to be enrolled in the study is:

- 1) Placebo group, 1.5 mL/kg – up to 30 screened female patients that corresponds to 26 randomizations and 24 completed cases
- 2) Placebo group, 2.4 mL/kg – up to 30 screened female patients that corresponds to 26 randomizations and 24 completed cases
- 3) Seroguard group, 1.5 mL/kg – up to 30 screened female patients that corresponds to 26 randomizations and 24 completed cases
- 4) Seroguard group, 2.4 mL/kg – up to 30 screened female patients that corresponds to 26 randomizations and 24 completed cases

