9.5 Procedures for accounting absent, unevaluable and doubtful data

At monitoring visit in the clinical site, monitoring officers authorized by the Sponsor will perform analysis of CRFs of the study subjects to check for absence of the required data. In case of absence of data in CRF and presence of respective information in the primary documentation, questions to the Investigators and assignments for elimination of non-conformities will be sent.

When checking database of the study results, a statistician authorized by the Sponsor and the Principal Investigator will perform analysis with respect to doubtful, omitted and unevaluable data by results of which the questions to the Investigators will be sent.

When applicable, the Investigators will eliminate the revealed errors in the CRF and inform the Principal Investigator and authorized representatives of the Sponsor on it. If the errors found in data will be impossible to be corrected after completion of female patient participation in the study, during statistical analysis of data, an analysis of sensitivity of the resulting parameters to presence

of doubtful data will be performed. Information on omitted, doubtful and unevaluable analysis of data will be provided in the final report on the clinical study.

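### Dosed women withdrawn before Visit 3 stay in the main ITT set with no planned Day-30 MRI, and section 9.5, cited for their data, does not say how those data are analysed

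*Protocol*

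**What the plan says.** **Treatment and analysis set.** Section 6.3.1 has study treatment given once, at the final stage of surgery at Visit 1. Section 9.7.1 makes ITT the main set and puts in it every randomised woman who received study drug, whatever her later compliance.

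**Withdrawal.** Under 5.3.1, detection of a withdrawal reason removes the woman at that stage. Section 6.2.2 requires withdrawal when prohibited therapy is needed or found. Section 5.3.4 plans no follow-up of withdrawn women other than for adverse reactions. Section 4.2.4.4 adds follow-up for women who leave voluntarily and for those with adverse reactions, until their condition resolves or stabilises; it promises no MRI.

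**Their data.** Section 5.3.3 says that they "will not be replaced by new ones, and their data will be considered in the final analysis (see section 9.5"). Section 5.3.2 says of a dosed woman that "her data collected before the moment of withdrawal/exclusion from the study will be analyzed during analysis of safety and, if possible", for efficacy, and that approaches to data on participants who "early terminated their participation in the study are described in section 9.5". Section 9.5 itself covers data queries, correction of errors and, for errors that cannot be corrected, "an analysis of sensitivity of the resulting parameters to presence" of doubtful data.

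**Which MRI.** Section 4.2.4.2 heads the last visit "Visit 3 (30±4) Evaluation of safety and efficacy". The synopsis, 4.5 and 7.2 also place efficacy at Day 30±4 or Visit 3. The primary endpoint in 4.1, 7.1 and 9.1.2 refers only to a repeated MRI. Section 4.2.4.4 says: "Visit of withdrawal from the study will be similar to completion Visit 3 by contents". That visit includes an MRI, on the day of withdrawal for inpatients or within 5 days of the withdrawal becoming known after discharge, unless the woman refuses.

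**The concern.** After a single instillation there is no treatment left to stop. Withdrawal therefore protects nothing in the treatment comparison; it only ends measurement. The plan keeps these women in its main denominator and stops collecting the outcome that the denominator needs. A statistical analysis plan can decide how to count a woman without a Visit 3 MRI, but it cannot recover a scan that was never taken.

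The MRI that she does have may fall within days of adhesiolysis. The documents do not say how a scan at that time reads compared with one at Day 30. Whether it may stand in for the repeated MRI is not stated, and the section cited as settling the analysis of these women does not do so. In arms of 26, two or three women counted one way or the other matter against a 5-point margin.

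**Working it through.** **1. Follow the cross-reference.** Sections 5.3.2 and 5.3.3 both send the reader to 9.5. Section 9.5 contains queries, corrections and an unspecified sensitivity analysis for doubtful data. It does not mention withdrawal and gives no responder, non-responder, carry-forward or exclusion rule. The pointer is wrong.

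**2. Set the MRI passages side by side.** The synopsis, 4.2.4.2, 4.5 and 7.2 point to Visit 3. The endpoint definition does not name a visit. Section 4.2.4.4 makes the withdrawal visit similar in content to Visit 3. Section 5.3.3 says the data will be considered. Section 5.3.2 speaks of data collected before withdrawal, and of efficacy only where possible. The status of the early scan is unclear.

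**3. Number of women.** Section 9.2: "Expected withdrawal from the study will make 15% at screening and 10% after randomization". So 0.10 × 26 = 2.6 per arm, or 2 to 3, and 0.10 × 104 = 10.4 overall. Two women are 2/26 = 7.7 points of an arm's response rate; three are 3/26 = 11.5 points. At the planned rate this is an upper figure: women withdrawn before dosing are outside ITT, and women who withdraw consent cannot be recovered.

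**4. The plan's own sample size.** Inputs: p1 = 45%, margin 5%, one-sided 5%, power 80%. The usual formula with p0 = 10% (synopsis) gives

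[0.45×0.55 + 0.10×0.90] × ((1.645 + 0.842)/0.30)² = 23.18, rounded up to 24.

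This matches the stated 24 completed cases, for which 26 are randomised. Section 9.2 gives p0 = 5% instead, so both values are carried below.

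**5. Effect of the classification.** Of 26 women per arm, k are affected and a share r of them is counted as responders:

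- p1* = (0.45(26−k) + kr)/26
- p0* = (p0(26−k) + kr)/26
- power = Φ[(p1* − p0* − 0.05)/√(p1*(1−p1*)/26 + p0*(1−p0*)/26) − z]

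Example, p0 = 10%, k = 2, r = 0: p1* = 0.4154, p0* = 0.0923, standard error 0.1121, ratio 0.2731/0.1121 = 2.436. With z = 1.645, power = Φ(0.791) = 78.6%.

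| Decision rule | p0 | None affected | Two per arm, non-responders | Two per arm, responders |
|---|---|---|---|---|
| One-sided 5% (z = 1.645) | 10% | 83.8% | 78.6% | 72.0% |
| One-sided 5% | 5% | 95.0% | 91.8% | 85.9% |
| Two-sided 95% CI limit above 5% (9.1.2; z = 1.96) | 10% | 75.0% | 68.3% | 60.6% |
| Two-sided 95% CI limit above 5% | 5% | 90.8% | 86.0% | 77.7% |

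The difference between the two decision rules at none affected (83.8% against 75.0%) has nothing to do with withdrawals. Observed cases only, 24 per arm, p0 = 10%, one-sided 5%: 81.2%.

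**The case against.** **The classification rule belongs to the statistical analysis plan.** Section 9.1 says so: "A complete analysis will be described in the plan of statistical analysis". This stands. A reader might infer that the plan has no rule for these women at all; the documents do not support that, because the analysis plan is not shown. What remains is that 5.3.2 and 5.3.3 state that 9.5 holds the approach and it does not. Correcting the pointer would cure that part. It would not cure the loss of the Day-30 scan, which is a matter of data collection.

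**The text already places efficacy at Visit 3.** Largely true, and 4.2.1 likewise ties the full efficacy evaluation to the repeated MRI after follow-up. No passage calls the withdrawal scan an efficacy reading, and 5.3.2 does not expressly bar it. So the passages are unreconciled; a reader who calls them a flat contradiction goes too far.

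**Few scans are recoverable.** Also fair. Conversion and the need for a drain arise during surgery, mostly before dosing. Consent withdrawals are out of reach, and a scan after repeat surgery is hard to interpret. Ten scans is a ceiling, not an expectation.

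**The sample size allows for attrition.** It does: 24 completers give 81.2% at a 10% placebo rate. At 5%, one-sided power stays above 80% in every scenario in the table.

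**Conclusion.** The point holds as a design weakness that should be corrected. The rules as written lose primary outcomes in the main analysis set after a one-time treatment, and no later analysis document can restore them. The faulty pointer to 9.5 and the unclear status of the early MRI add to this; alone they would be minor.

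With two women affected per arm, non-responder counting costs about 3 to 7 points of power and responder counting about 9 to 14, depending on the placebo rate and the decision rule. These figures assume all 26 per arm are dosed, equal losses in the arms, a 45% active rate and a normal approximation. All-responder and all-non-responder are the two ends of the range.

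A reader might infer that early scans favour Seroguard or raise the false-positive rate. The documents do not support this: they do not say how an early scan reads, nor that withdrawals would differ between arms. The direction of any bias is unknown. Nor do the figures show that withdrawals alone leave the trial underpowered, since that depends on which of the two stated placebo rates applies.

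**What to change.** 1. **Keep the Visit 3 MRI.** For dosed women who have not withdrawn consent, and where MRI remains possible and appropriate in the investigator's judgement, collect the already scheduled Visit 3 MRI as data collection only. The sponsor reconciles 4.2.4.4, 5.3, 5.3.2 to 5.3.4 and 6.2.2 accordingly, without changing any clinical rule.
2. **Name the scan.** State in 4.1, 7.1 and 9.1.2 that the primary endpoint uses the Visit 3 (Day 30±4) MRI, and that a withdrawal-visit MRI outside that window does not establish response.
3. **Make 9.5 true.** Either put in it one classification rule for dosed women without a Visit 3 MRI, the same in all arms (for example non-responder, with an observed-case sensitivity analysis), or correct the pointers in 5.3.2 and 5.3.3 to the statistical analysis plan.

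Cost: wording in these sections and a few scans, at most about ten, that are already in the schedule. Non-responder counting lowers stated power slightly: 78.6% against 81.2% for observed cases with two missing per arm (p0 = 10%, one-sided 5%).
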